11.3.2 Secondary Analysis

1) The relationship between methadone concentrations/other PK parameters and endpoints of change in pupillometry, observed sedation levels, thermal pain tolerance thresholds, change in VAS from pre to post dose, and change in respiratory rate will be evaluated using standard descriptive statistics. Descriptive summaries of the endpoints predose, postdose, end of follow-up will be presented. The change between time points also will be presented, along with the 95% CI, t-test, and p-value.

2) The following endpoints will be analyzed in the safety analyses:

Incidence of safety related events

- A. AE related to study procedure
- B. SAE related to study procedure
- C. SUSAR related to study drug
- D. Safety Events of Special Interest (QTc prolongation)

In addition, changes in QTc interval will be assessed over time.

All AEs recorded during the study period will be coded with Medical Dictionary for Regulatory Activities (MedDRA) Version March 2018. Summaries of AE will be tabulated for the following types:

- A. Number (%) of participants with any AE
- B. Number (%) of participants with any SAE
- C. Number (%) of participants withdrawn from treatment due to SUSAR

All summaries will be reported in total and by study site.

Additional analyses (e.g., Exposure-Response [safety] analysis) and summaries may be derived if deemed appropriate and will be further described in the SAP.

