3 OBJECTIVES AND OUTCOME MEASURES

	Objective	Measures	Endpoints
Primary	Characterize the PK of methadone hydrochloride injection	Plasma concentrations	1. Clearance (CL) 2. Volume of distribution (Vz) 3. Half-life (t _{1/2}) 4. Area under the curve (AUC) 5. Maximum concentration (C _{max}) 6. Time to maximum concentration (T _{max}) 7. Minimum concentration (C _{min}) 8. Elimination rate constant (k _e)
Secondary	Characterize the PD effect of methadone hydrochloride injection	1. Dark-adapted pupillometry 2. Observed sedation 3. Thermal pain tolerance thresholds 4. Subjective self-assessment of methadone effects using visual analog scale (VAS)	Change in pupillometry, observed sedation, thermal pain tolerance thresholds, and VAS from pre-dose to each post-dose time point
Secondary	Characterize the tolerability of methadone hydrochloride injection	1. Adverse events (AEs) 2. Serious adverse events (SAEs) 3. Suspected Unexpected Serious Adverse Reactions (SUSARs) 4. Safety events of special interest (QTc)	For AEs, SAEs, SUSARs: Proportion of participants from baseline to the end of safety follow-up For SESI: Change in QTc from baseline to the end of safety follow-up
Exploratory	Characterize exposure-response relationships	Plasma concentrations and VAS	Correlation of plasma concentrations to VAS score at each post-dose VAS time point

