5.2 Inclusion/Exclusion Criteria

Inclusion Criteria	
1. 18 to < 40 years of age at the time of enrollment2. Provides informed consent
Exclusion Criteria	
1. History of cardiac dysfunction2. History of or current QTc prolongation, defined as > 470 ms in males and > 480 ms in females3. Known hypersensitivity to methadone hydrochloride or any other ingredient in the methadone hydrochloride injection4. Known acute bronchial asthma or hypercarbia (history of known PaCO₂ above 45 mm HG)5. Receipt of a serotonergic drug or bupropion within 7 days prior to study enrollment6. Receipt of benzodiazepines, muscle relaxants, or other opioids within 7 days prior to study enrollment7. Receipt of a moderate or strong CYP2B6 inhibitor or inducer – either prescription or non-prescription medications, herbals,³⁴ or foods known to be metabolized by or affecting CYP2B6 within 30 days prior to study enrollment
a) CYP2B6 inhibitors include clopidogrel, prasugrel, thioTEPA, ticlopidine, voriconazole, macrolide antibiotics, azole-antifungal agents, fluconazole, Alstonia boonei, Mangifera indica, and Picralima nitidab) CYP2B6 inducers include artemisinin antimalarials, barbiturates, carbamazepine, cyclophosphamide, efavirenz, lopinavir, methimazole, nelfinavir, phenobarbital, phenytoin, primidone, rifampicin/rifampin, ritonavir, abacavir, amprenavir, nevirapine, telaprevir8. Receipt of zidovudine, desipramine, or other drugs that may increase serum concentration when combined with methadone within 30 days prior to study enrollment9. Known or suspected gastrointestinal obstruction, including paralytic ileus10. Significant respiratory depression (respiratory rate less than 8 breaths/min or oxygen saturation (SpO₂) <95%)11. BMI ≥ 33 and BMI ≤ 1712. Known history of moderate-to-severe liver (Child Class B or C) or kidney disease (serum creatinine > 1.5)13. Known history of drug or alcohol addiction (prior or present addiction or treatment for addiction)14. Females who are pregnant or nursing

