6.8.4 Observed Sedation, MOAA/S

Sedation will be observed and recorded by the study team using the Modified Observer's Assessment of Alertness/Sedation (MOAA/S).

Modified Observer's Assessment of Alertness/Sedation [MOAA/S]	
Responsiveness	Score
Responds readily to name spoken in normal tone	5 (alert)
Lethargic response to name spoken in normal tone	4
Responds only after name is called loudly and/ or repeatedly	3
Responds only after mild prodding or shaking	2
Responds only after painful trapezius squeeze	1
Does not respond to painful trapezius squeeze	0

Refer to MOP for details.

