6.8.7 Summary of Study-specific Procedures

Table 5. Schedule of study-specific procedures

Elapsed Time After Dose (hh:mm)	Pupillometry, Dark-Adapted	Vital Signs RR, CO ₂ , HR	Vital Signs BP, SpO ₂	Observed Sedation, MOAA/S	Thermal Pain Threshold	Subjective Self Assessment, VAS
Baseline draw	X	X	X	X	X	X
Start IV dose						
0:02 ± 0:01	X	X			X	
0:04 ± 0:01	X	X		X		X
0:06 ± 0:01	X	X			X	
0:08 ± 0:01	X	X				
0:10 ± 0:01	X	X	X	X	X	X
0:12 ± 0:01	X	X				
0:15 ± 0:01	X	X				
0:20 ± 0:01	X	X				
0:30 ± 0:02	X	X				
0:40 ± 0:02	X	X		X	X	X
0:50 ± 0:02	X	X				
1:00 ± 0:05	X	X	X	X	X	X
1:30 ± 0:05		X		X		X
2:00 ± 0:10	X	X	X	X	X	X
3:00 ± 0:10		X		X		X
4:00 ± 0:10	X	X	X	X	X	X
6:00 ± 0:30		X	X	X		X
8:00 ± 0:30	X	X		X	X	X
10:00 ± 0:30		X		X		X
12:00 ± 0:30	X	X	X	X	X	X
18:00 ± 0:30						
24:00 ± 1:00	X	X		X	X	X
30:00 ± 1:00	X	X	X	X	X	X
48:00 ± 8:00	X	X	X	X	X	X
72:00 ± 8:00	X	X	X	X	X	X
96:00 ± 8:00	X	X	X	X	X	X

Some timepoints have multiple tasks scheduled. It is suggested that the tasks be prioritized in order of: obtaining the PK sample, pupillometry, vital signs, observed sedation, thermal pain threshold, and subjective self-assessment. These tasks are not all performed during all the timepoints, please follow Tables 4 and 5 above. The research staff does have the discretion to perform the task order according to their trained judgement as long as they are within the timepoint parameters.

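### The t-test and 95% CI planned for change in MOAA/S can be undefined, or include impossible values, when few participants leave the top score of 5

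*Combined protocol and SAP*

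**What the plan says.** The objectives table in Section 3 defines the secondary pharmacodynamic endpoint as "Change in pupillometry, observed sedation, thermal pain tolerance thresholds, and VAS from pre-dose to each post-dose time point". Section 11.3.2 lists the "endpoints of change in pupillometry, observed sedation levels, thermal pain tolerance thresholds, change in VAS from pre to post dose", adds respiratory rate, plans descriptive summaries, and continues: "The change between time points also will be presented, along with the 95% CI, t-test, and p-value". No endpoint is exempted, and no ordinal, exact or non-parametric method appears anywhere.

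Section 6.8.4 names the sedation instrument: "Sedation will be observed and recorded by the study team using the Modified Observer's Assessment of Alertness/Sedation (MOAA/S"). Its top category, 5, is "Responds readily to name spoken in normal tone"; its bottom category, 0, is "Does not respond to painful trapezius squeeze". In Section 6.8.7, "Table 5. Schedule of study-specific procedures" marks MOAA/S at baseline and at 17 post-dose times, from 0:04 to 96:00.

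Section 11.3 plans counts and percentages for discrete variables, with race and sex as its examples. It leaves detailed secondary methods to a statistical analysis plan to be written before data lock.

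**The concern.** A t interval for mean change treats the differences as roughly symmetric on an unbounded scale. MOAA/S has six ordered categories, and score 5 asks only for a ready response to one's name. Participants are healthy adults, and Section 5.2 excludes "Receipt of benzodiazepines, muscle relaxants, or other opioids within 7 days prior to study enrollment". Section 7.3 also bars alcohol for 24 hours before dosing. A baseline of 5 for nearly everyone is therefore a strong inference, though no baseline score is stated.

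From that start, a participant's change is zero or negative. At times when few have left score 5, the differences are mostly zeros with a few small negatives. The planned output may then have a blank test, an interval of zero width, or an interval that reaches above the top of the scale. This would affect the readability of a secondary endpoint that Section 3 wants at each post-dose time, so at up to 17 times. The late visits (48, 72 and 96 hours) are the likeliest places for every score to be 5, and 96 hours is the end of follow-up that Section 11.3.2 singles out for summary.

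**Working it through.** **The plan's own figure.** The only sample-size figure, in Section 11.6, is for clearance: 15 participants, CV 23% to 38%, 95% CI within 60% to 140% of the geometric mean. A simple log-normal check uses σ = √ln(1 + CV²) and CI = exp(±t₀.₉₇₅,₁₄ σ/√15). It gives 88% to 113% at CV 23% and 82% to 123% at CV 38%. The stated figure holds. No sample size, SD or effect size is given for MOAA/S.

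**Inputs for MOAA/S**
- n = 20 (about 20 participants, Section 5.1); 95% confidence (Section 11.3).
- The endpoint is change from each participant's own pre-dose value (Section 3), so the t-test is in effect paired, although the word is not used.
- Assumed: all participants at 5 at baseline, and k of them down by exactly one point at a given time. The documents give no distribution, so k is varied.

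**Formulas.** Mean change = -k/n. SE = √[(k/n)(1 - k/n)/(n - 1)]. 95% CI = mean ± t₀.₉₇₅,₁₉ × SE, with t₀.₉₇₅,₁₉ = 2.093. For k = 1, SE = √(0.05 × 0.95/19) = 0.050, and the CI is -0.05 ± 0.105. The last column is the Clopper-Pearson interval for the proportion below 5.

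| k of 20 | Mean change | t-based 95% CI | Below 5 (exact 95% CI) |
|---|---|---|---|
| 0 | 0 | SD = 0, test undefined | 0% (0 to 16.8%) |
| 1 | -0.05 | -0.155 to +0.055 | 5% (0.1 to 24.9%) |
| 2 | -0.10 | -0.244 to +0.044 | 10% (1.2 to 31.7%) |
| 3 | -0.15 | -0.321 to +0.021 | 15% (3.2 to 37.9%) |
| 4 | -0.20 | -0.392 to -0.008 | 20% (5.7 to 43.7%) |
| 6 | -0.30 | -0.520 to -0.080 | 30% (11.9 to 54.3%) |

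Upper limits above zero occur at k = 1 to 3 and are impossible from a baseline of 5. The exact interval is defined in every row and stays within 0% to 100%.

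**Coverage.** Let the true proportion falling by one point be p, so that the true mean change is -p. Summing binomial probabilities over k = 0 to 20, and counting the zero-width interval at k = 0 as a miss, gives:

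| p | Test undefined | CI reaches above 0 | Coverage of nominal 95% CI |
|---|---|---|---|
| 5% | 36% | 63% | 64% |
| 10% | 12% | 75% | 88% |
| 20% | 1% | 40% | 92% |
| 30% | 0.1% | 11% | 95% |
| 50% | 0% | 0.1% | 96% |

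At p = 5% and 10% nearly all of the shortfall is the no-fall sample: 0.95²⁰ = 0.358 and 0.90²⁰ = 0.122, against total non-coverage of 0.359 and 0.124. Coverage is about nominal at p = 30%, where 30% × 20 = 6 falls are expected.

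**Sensitivity.** With n = 15, k = 3 gives -0.429 to +0.029, and the chance of an undefined test at p = 5% is 46%. Deeper falls move the limits: four participants falling by 2, 1, 1 and 1 points (n = 20) give -0.507 to +0.007, so an impossible upper limit can also occur at k = 4.

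**The case against.** Three arguments on the other side have weight.

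First, the harm is conditional. Section 2.4 lists sedation among the most frequent adverse reactions, so many participants may fall near peak effect, and there the t interval behaves acceptably. This stands: the fault belongs to time points with few falls, not to all 17.

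Second, Section 11.3 already plans counts for discrete variables and defers detail to the SAP. Part of the remedy may therefore be intended. But MOAA/S is not named there, the counts are descriptive only, and nothing displaces the explicit t-test sentence.

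Third, little rests on this result. The study is an open-label, single-dose PK study, no decision rule uses a MOAA/S p-value, and the halting rules in Section 9.2 use SAEs and severe reactions. This stands and limits the importance of the point.

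A reader might also infer that the t-test overstates the evidence for sedation. At k = 4 it gives p = 0.042, where an exact sign test gives 2 × 0.5⁴ = 0.125. The documents do not support that inference. If everyone starts at 5, no true change means that nobody falls, and a single fall refutes it. The sign test's null, with rises and falls equally likely, cannot occur either. Neither p-value is a standard for judging the other, so a sign test is not a sound replacement.

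**Conclusion.** The planned CI and t-test do not suit MOAA/S and should be replaced for that endpoint. When few participants leave score 5, they can give an undefined test (no falls) or an interval containing impossible values (one to three one-point falls among 20). The nominal 95% interval has coverage of about 64% and 88% at true falling proportions of 5% and 10%, chiefly because it collapses when nobody falls. The difficulty fades at about six or more falls.

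These figures rest on three assumptions: a baseline of 5 for all, one-point falls, and n = 20. The first is inferred from the population. The pattern is the same at n = 15, and deeper falls shift the limits. It would go too far to say that the analysis will fail at every time point, or that its p-values are shown to be wrong. The consequence is confined to one secondary endpoint; the primary PK analysis and the clearance sample size are untouched.

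**What to change.** State in Section 11.3.2, and carry into the SAP, that the CI, t-test and p-value for change do not apply to MOAA/S. For MOAA/S report instead:

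- at baseline and each post-dose time, the number and percentage of participants at each score from 0 to 5;
- at each time, the proportion below 5 with an exact (Clopper-Pearson) 95% CI;
- the lowest post-dose score per participant, tabulated by score.

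No p-value is needed. The baseline row will show whether the assumed start at 5 holds. The cost is SAP wording only: the scores are already scheduled, and no visit, assessment or participant is added. The change should be made before data lock.

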11.3.3 Exploratory Analysis

A tabular or graphical data exploration of the relationship between safety endpoints (i.e., the occurrence of selected AEs) by methadone steady state exposures (e.g., AUC and Cmax) quantiles will be evaluated. The relationship between these steady-state exposures and the probability of experiencing AEs with possible covariates will be evaluated using logistic regression analysis.

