5 STUDY POPULATION

5.1 Selection of the Study Population/Sample Size

Approximately 20 evaluable healthy volunteers 18 to < 40 years old will be enrolled. Sex will be approximately equally distributed. Participants will be recruited from the greater Durham and Triangle community and a healthy volunteer registry in the DEPRU. Participants will be compensated.

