7.1.1 Dosage and Dose Timing

Each participant will be administered a single dose of IV methadone at 0.1 mg/kg per measured body weight. The single dose will be calculated to the closest 0.1 mg.

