11.6 Sample Size Considerations

For the primary objective, the sample size is based on the ability to precisely estimate the clearance in adults using population PK techniques. For IV methadone in healthy adult volunteers, we anticipate a CV% of 23 and 38% for R and S-enantiomers, respectively.¹⁵ Based on this range of CV%, 15 participants will be adequate to precisely describe CL with a 95% CI (confidence interval) within 60% and 140% of the geometric mean.

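### The exposure-AE logistic regression in about 20 people makes no provision for sparse events; a Firth-penalised fit would stay finite and be close to unbiased on average

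*Combined protocol and SAP*

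**What the plan says.** Section 11.3.3 (Exploratory Analysis) first plans a table or graph of "the relationship between safety endpoints (i.e., the occurrence of selected AEs) by methadone steady state exposures", by exposure quantile, with AUC and Cmax as examples. It then commits to a model: "the probability of experiencing AEs with possible covariates will be evaluated using logistic regression analysis". It does not say which AEs are selected, which or how many covariates may enter, how the model is fitted, or what happens if an AE has no events or the data separate.

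The data available to that model are set elsewhere. Section 5.1: "Approximately 20 evaluable healthy volunteers 18 to < 40 years old will be enrolled", and "Sex will be approximately equally distributed". Section 7.1.1: "Each participant will be administered a single dose of IV methadone at 0.1 mg/kg per measured body weight". Section 11.6 justifies the sample size for clearance only: "15 participants will be adequate to precisely describe CL with a 95% CI (confidence interval) within 60% and 140% of the geometric mean".

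Section 11.3 promises detailed methods in a SAP before data lock, and Section 11.3.2 says exposure-response safety analyses may be described further there. The supplied text contains no such further description.

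**The concern.** A logistic model fitted to 20 binary outcomes is fragile when events are few. If every event falls in one sex, the likelihood keeps rising as the sex coefficient grows, and no finite maximum-likelihood estimate exists. The same happens to the exposure slope if all participants with the AE have higher exposure than all those without it. When the fit does converge and a real association exists, small-sample bias pushes the log odds ratio away from zero on average. With one dose level and no control arm, exposure varies only between people, so the design supplies no additional contrast.

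At stake is how readable the trial's exposure-safety statement will be. A software default could report an enormous odds ratio with a meaningless interval, or one inflated by the fitting method. With covariates left open, the model could also be chosen after the data are seen.

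**Working it through.** **1. The plan's own figure.** Section 11.6 states "we anticipate a CV% of 23 and 38% for R and S-enantiomers, respectively". On the log scale σ = √ln(1 + CV²), and the interval limits relative to the geometric mean are exp(± t(0.975, n−1)·σ/√n). For n = 15, t = 2.145.
- CV 23%: σ = 0.227, half-width 0.126, limits 88.2% to 113.4%.
- CV 38%: σ = 0.367, half-width 0.203, limits 81.6% to 122.6%.

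Both lie inside 60-140%, so 15 is adequate for clearance as stated. The calculation does not address the AE model.

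**2. Separation by sex, in closed form.** Inputs: n = 20 and roughly equal sexes (Section 5.1), taken as 10 and 10. AE incidence p is not in the documents and is assumed from 10% to 50%. With no true effect, the chance that one sex has no events is q = (1 − p)^10. The chance that all events fall in one sex is 2q(1 − q). The chance of no events at all is (1 − p)^20.

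| p | q | all events in one sex | no events |
|---|---|---|---|
| 10% | 0.349 | 45% | 12% |
| 15% | 0.197 | 32% | 4% |
| 20% | 0.107 | 19% | 1% |
| 30% | 0.028 | 5.5% | 0.1% |
| 50% | 0.001 | 0.2% | about 0 |

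At 50% the mirror case (all non-events in one sex) is equally likely, giving 0.4% in total.

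**3. Simulation of the fit.** Setting: n = 20, standardised log exposure, with or without a sex term unrelated to the AE, 1,500 trials per setting. Separation is detected by linear programming.
- Exposure plus sex, no true effect: separation, so that some coefficient is infinite, in 44%, 31%, 21% and 6% of trials at p = 10%, 15%, 20% and 30%, and 1% or less at 50%. This agrees with step 2.
- Exposure slope itself undefined or infinite with sex in the model, counting trials with no events (OR 1 to 2): 18-25% at 10%, of which about 12 points are trials with no events; 4-6% at 20%; at most 2% at 30%; about 0 at 50%.
- Exposure only: separation about 3-6% at 10% and under 1% at 30% or more.

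**4. Bias in finite fits.** Assumed true OR of 2 per SD, so log OR = ln 2 = 0.693.
- Exposure only: mean maximum-likelihood slope 0.85-0.94. 0.85/0.693 = 1.23 and 0.94/0.693 = 1.36, so about 25-35% too large.
- With sex: mean 0.97-1.08. 0.97/0.693 = 1.40 and 1.08/0.693 = 1.56, so about 40-55% too large.
- The median is only about 8-13% high without covariates.
- True slope zero: means within 0.03 of zero in exposure-only fits, so no direction.

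The means are pulled by a long right tail and vary between runs. A second set of simulations over 5-50% incidence gave 0.86-1.08 (exposure only) and 1.01-1.30 (one binary covariate).

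**5. The alternative.** Firth's method maximises ℓ(β) + ½ log|I(β)|, which keeps every estimate finite under separation. In the setting of step 4 its mean slope was 0.62-0.72 against 0.693, with lower root mean squared error than maximum likelihood in every setting, including 30-50% incidence. Its median was about 10% below the truth.

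**The case against.** Four points can be made for leaving the text alone.

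- **The failing coefficient is mostly not the one of interest.** Section 11.3.3 asks about exposure, names no covariate and calls covariates only possible. A reader might infer that the exposure slope will often have no finite estimate. The documents do not support that: with exposure alone, separation is about 3-6% even at 10% incidence. This stands, and limits the point.
- **Incidence is unknown.** Section 2.4 lists sedation, nausea and dizziness among the most frequent reactions but gives no rates. If the selected AEs occur in 30-50% of participants, non-estimability is small. This also stands, although the prophylactic antiemetic in Section 7.3 means a high nausea rate cannot be assumed.
- **Upward bias is not assured in one data set.** A reader might infer that any finite estimate overstates the slope. It does so on average and only when an association exists. At OR 2 the estimate exceeded the truth in only about 49-61% of individual fits.
- **The analysis is exploratory and details are deferred to the SAP.** Maximum likelihood is inferred as the usual default; the text does not name it. Low power is no defect in an exploratory analysis, and the planned table or graph already covers rare AEs. A floor of 5 events and 5 non-events with exposure alone would cut separation to 0.2% or less, leaving Firth to correct only the average bias.

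What remains is that the section already commits to the regression and leaves covariates open, and that a better fitting method is available as a standard software option. The lower error with Firth holds at 30-50% incidence too, so the case does not depend on AEs being rare.

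**Conclusion.** The concern holds in limited form. Section 11.3.3 plans a model for sparse binary data in about 20 people with no sparse-event provision. Under ordinary maximum likelihood, the cost ranges from substantial (some coefficient infinite in about 44% of trials at 10% incidence with sex included) to negligible (1% or less at 50%). With a real association of OR 2 per SD, there is an average overstatement of about 25-35% with exposure alone or 40-55% with sex.

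These figures rest on assumed incidences, an assumed slope, a 10:10 sex split, covariates unrelated to the AE, and maximum likelihood as the default estimator. None of the incidences or slopes is in the documents.

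A reader might also infer that a faulty odds ratio would feed into paediatric labelling. Section 2.2 rests that aim on the PK/PD relationship, and the documents do not tie it to this exploratory regression. The use of steady-state exposure in a single-dose study is a separate matter, and correcting that wording would not resolve this one.

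**What to change.** In Section 11.3.3, replace the regression sentence with text to this effect:
- The exposure-AE model will be fitted by Firth-penalised (or exact) logistic regression with exposure as the main predictor. The odds ratio and its 95% CI will be reported as exploratory.
- At most one covariate, named in advance, may be added.
- An AE with fewer than a stated number of participants with or without the event will be shown only in the tabular or graphical display already planned. The sponsor should set the floor; 5 of each is an example, and a matter of judgement.

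The cost is a short edit and a standard software option. Firth shrinks the estimate slightly (median about 10% below the truth at OR 2), and there is little or no covariate adjustment. A floor of 5 would send many AEs to display only: with n = 20, the chance of 4 or fewer events is 96% at 10% incidence, 63% at 20%, 24% at 30% and 0.6% at 50%. No method can estimate a slope when nobody, or everybody, has the AE.
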